Progressive Supervised Home-based Strength Training in Children With Spastic Cerebral Palsy

NCT number: NCT03863197

Protocol data: 1 November 2021

Study protocol

Study outline

A waitlist randomized controlled trial (RCT) will be conducted to define the effects of a progressive resistance training (PRT) program for the knee extensor, knee flexor and plantar flexor muscle groups in children with spastic cerebral palsy (CP). A minimization technique will be used to divide participants in an intervention group, performing a 12-week PRT program and a waitlist control group, continuing usual care for 12 weeks first. After the control period, the participants were offered to participate in the intervention.

Participants

Participants will be recruited across Flanders in Belgium, through the CP reference center of the University Hospitals Leuven, pediatric physiotherapists, and special needs schools. Written informed consent will be obtained from the children's parents or legal guardian prior to the first assessment. The study is registered at Clinicaltrials.gov (NCT03863197) and was approved by local medical ethical committees of University Hospitals Leuven (s59945) and Ghent (EC/2017/0526). The inclusion criteria for participation are 1) a diagnosis of SCP, 2) age at baseline between 5 and 11 years and 3) level of I, II or III on the gross motor function classification system (GMFCS) (Palisano et al., 2008) . Exclusion criteria were 1) botulinum neuro-toxin A injections and/or lower leg casts in the past 6 months, 2) lower limb bony surgery in the past 2 years, 3) lower limb muscular surgery or selective dorsal rhizotomy at any time point, 4) inability to communicate in Dutch or English and 5) inability to understand instructions and cooperate during assessments and training.

For comparison of baseline data, a convenience sample of typically developing (TD) children will be recruited via hospital co-workers and students within the same age range of 5–12 years. The TD children could not have any known neurological or orthopedic lower limb problems. The TD children will only participate in one assessment of isometric strength, 3D freehand ultrasonography and functional strength (see below).

Study design

After enrollment and prior to the first assessment, participants will be assigned to the intervention or the control group through randomization by minimization. MinimPy will be used to randomize the participants based on age (2 levels: <8 years and >8 years) and GMFCS score (3 levels: I, II and III) (Saghaei, 2011). The allocation ratio will be 1:1 with probability set at 0.75. The biased coin minimization will be used as probability method and marginal balance as distance measure.

Assessments are planned in the University Hospitals and special needs schools, at baseline (PRE) and after the 12-week control or intervention period (POST). Training and assessments will always be

conducted on different days. Participants in the intervention group start training within 2 weeks after the baseline assessment. For both groups, the POST assessments will be performed within 1 week after the 12-week period. Blinding is not completely possible since participants and trainers are aware of group allocation. Assessors are also aware of group allocation during assessments but data will be anonymized before processing and analyses. The participants will be assessed by the same assessors (PRE and POST) and the data of one participant will be processed by the same processor.

Piloting for the feasibility of the measurements and parameter extraction was done through prior and parallel investigations. The exercises used during the training were piloted through iterations with strength and conditioning specialists to ensure correct exercise selection and also with senior pediatric physiotherapists and their patients to ensure the applicability in targeted population of children with SCP.

Sample size

At the moment of trial design (2018), no data were available on an RCT investigating changes in muscle size after PRT in a population of children with SCP. Therefore, effect sizes (d) of systematic reviews and meta-analyses reporting muscle strength outcomes after PRT were used. Reported effect sizes were moderate ($d=0.53$) (Ryan et al., 2017) and large ($d=1.050$ and $d=1.105$) (Park & Kim, 2014). Based on a large effect size of $d=0.8$ with the probability of making a type I error set equal to or less than 1% ($p\leq 0.01$) and a power of 80%, an independent samples t-test with common standard deviation required 39 independent observations per group to compare the evolution over time between the intervention and control groups. To account for the possibility of clustered legs in bilaterally affected participants a design effect (Killip et al., 2004) was calculated resulting in an estimated sample size of clustered observations per group with following formulas:

$$\text{Design effect} = 1 + \rho * (m-1),$$

where ρ is the intraclass correlation and m the cluster size, and,

$$\text{Estimated sample size of clustered legs} = \text{estimated sample size of independent observations} * \text{design effect} = m * \text{number of participants}$$

With a cluster size of $m=2$ (2 legs per bilaterally affected participant) and an intraclass correlation coefficient of $\rho=0.1$, based on literature of general health parameters (Adams et al., 2004), the estimated design effect was 1.1, resulting in 43 clustered legs, or 22 bilaterally affected participants per group. A group including both uni- and bilaterally affected children would require a sample size between 39 and 43.

Intervention

Participants assigned to the control group will continue their usual care. Participants assigned to the intervention group will undertake 3 to 4 PRT sessions per week (alternating), on non-consecutive days, for 12 weeks, resulting in a total of 42 scheduled sessions. The PRT program will be explained during a visit to the physiotherapist(s) and parent(s). After a familiarization phase of up to 3 sessions, the official PRT starts. At least 1 session per week will be performed under the supervision of the physiotherapist(s). The remaining sessions will be completed at home under the supervision of a parent or guardian. We will create a patient-specific PRT program through the online software platform Skill-Up (www.Skill-up.com) and ask the participants to log each PRT session in a training diary. Throughout the 12-week period, the PRT program will be supervised through phone calls, e-mails, and targeted visits to check adherence and progress exercises by trainers with a background in human movement sciences. Participants in the intervention group were invited for an interim

assessment after 6 weeks, which was also used as an additional moment to evaluate and adjust the intensity of the training program.

The PRT program, targeting strength and hypertrophy of knee extensors, knee flexors and plantar flexors, will be prescribed in close consultation with the personal physiotherapist(s) to ensure feasibility for each participant. The general session design recommendations include a 5-minute dynamic warm-up and a 5-minute cool-down. Depending on the participants' abilities, the PRT will start with 1-3 functional multi-joint exercises, followed by 2-3 single-joint exercises targeting the specific muscle groups, all performed without orthotics. Following international guidelines for youth resistance training of the National Strength and Conditioning Association, as well as CP-specific recommendations, the initial exercises start at a training volume of 3 sets of 10 repetitions, aiming at an exercise intensity of 60 to 80% of the estimated 1-repetition maximum, with a rest period in between sets of at least 1 minute (Faigenbaum et al., 2009; Lloyd et al., 2014; Noorduyn et al., 2011; Verschuren et al., 2016). The most difficult exercise that could be performed, with the maximal load that could be lifted, for the defined number of repetitions and sets was defined through trial and error (Moreau, 2020). Throughout the training program, exercise difficulty was increased. Thereto, physiotherapists will be encouraged to regularly test the difficulty of the exercises, i.e. at least biweekly, by asking a maximum performance in the last set, based on exercise execution and fatigue. The intensity will be modified by the trainers or the physiotherapist(s) if the last set exceeded 15 well-executed repetitions. Exercise modification options are dependent on the exercise and include addition of weight in a weighted vest (0.5kg increments up to 10kg), use of a stronger resistance band (5 colors ranging from light to very heavy), increase of ankle weight (1.0, 1.5 or 2.0kg), or selection of a more challenging exercise. The number of sets and repetitions performed, modifications or compensations, perceived fatigue at the end of the session and potential adverse events will be noted in the training diary.

Assessments and outcome measures

1. Participant characteristics

Age, body mass and height will be recorded for the participants at each assessment. Usual care and treatment history will be recorded at the PRE-assessment using standardized in-house questionnaires. A routine clinical examination regarding the investigated muscle groups will be performed, including passive joint range of motion, spasticity, manual muscle strength and selective motor control (SMC), based on standard clinical scales (Bohannon & Smith, 1987; Boyd, 1999; Gage et al., 2009; Matthews, 1977). These clinical examination parameters will be used to define the most affected leg for bilaterally affected children. If both sides are equally affected, the right leg will be used. Lower limb SMC will be assessed with the selective control assessment of the lower extremity total limb score (Fowler et al., 2009). Assessments will be performed in the same order, starting with clinical examination and muscle morphology, followed by isometric and functional strength and lastly gross motor function and walking capacity.

2. Isometric strength assessments

Knee extensor, knee flexor and plantar flexion maximum voluntary isometric contractions were collected with a fixed dynamometer in a previously described, custom-designed chair (Goudriaan et al., 2018). The dynamometer is positioned at 75% of the lower leg and foot length, and the level arm distance is measured between this position and the joint axis. After a test trial, we aim to collect 3 well executed maximum voluntary isometric contractions with a duration of 3 to 5 seconds. Standardized verbal encouragement and visual feedback will be provided throughout the isometric contraction. The protocol includes periods of rests of at least 10 seconds between repeated

assessments and of at least 2 minutes between different muscle groups. Peak force is extracted from each trial with a custom-written MATLAB script and maximal joint torque (in Nm) will be calculated by multiplying peak force with the lever arm and taking the average of the 3 trials. Knee and plantar flexion maximal voluntary isometric contractions are corrected for gravity by subtracting the gravitational torque in rest from the outcomes. Maximal joint torque will be normalized by dividing it by body weight (Nm/kg).

3. Three-dimensional freehand ultrasonography

A previously validated 3-dimensional freehand ultrasonography technique will be used to evaluate muscle morphology, combining a 2-dimensional B-mode ultrasonography device (Telemed-Echoblastar 128 Ext-1Z, with a 5.9 cm 10MHz linear ultrasound transducer, Telemed, Ltd, Lithuania) with a motion tracking system (Optitrack V120:Trio, NaturalPoint, Inc, Corvallis, Oregon, USA) (Cenni et al., 2016). Ultrasound settings will be kept constant throughout the study period, at a frequency of 8MHz, with a focus of 3cm, a gain of 64%, a dynamic range of 56 dB and unaltered time-gain compensation. Depth can vary between 5cm and 7cm, adjusted to muscle size. The m. rectus femoris and m. tibialis anterior will be scanned in supine position with a triangular cushion underneath the calf, providing approximately 25 degrees of knee and hip flexion. The m. semitendinosus and m. medial gastrocnemius will be scanned in prone position with a triangular cushion underneath the shank, providing 25 degrees of knee flexion and an unconstrained ankle angle. STRADWIN software (version 6.0; Mechanical Engineering, Cambridge University, Cambridge, UK) will be used for data acquisition, generation of 3-D datasets, and data processing. Data processing will be performed by experienced processors, drawing equally spaced transverse plane segmentations throughout the 3-D datasets, which will be interpolated with an automatic cubic planimetry technique resulting in the muscle volume (in mL) (Treece et al., 1999). Muscle length (in mm) will be defined by calculating the linear distance between muscle origin and muscle tendon junction. Both muscle volume and muscle length will be normalized to fibula length to correct for skeletal growth (mL/cm and cm/cm). The echo-intensity (EI) from ultrasound images will be used as an indication of intrinsic muscle quality, with higher EI-values representing an increased ratio of non-contractile vs. contractile tissue (Pitcher et al., 2015; Young et al., 2015). EI (expressed in arbitrary units) will be computed as the average value throughout the interpolated reconstruction of the muscle.

4. Functional strength assessments

Endurance functional strength will be assessed with 30-s repetition maximum tests including bi- and unilateral heel raise, sit-to-stand, and lateral step-up, as previously described (van Tittelboom et al., 2021). Participants completed as many repetitions as possible in 30 seconds. Each test will be 3 times and the average taken as final score. Explosive strength will be evaluated with a standing long jump, with both feet together, which will also be repeated 3 times and the scores averaged. The use of orthoses will not be allowed, as the PRT program will also be performed without orthoses.

5. Gross motor function and walking capacity

Gross motor function will be evaluated with the Gross Motor Function Measure-Item Set (Brunton & Bartlett, 2011) and the Gross Motor Ability Estimator 2 used to estimate the final score. The 1-minute walk test, performed on an indoor 20-m track, will be used to assess walking capacity (Chrysagis et al., 2014; McDowell et al., 2009). The participant will be instructed to walk as fast as possible without running and the distance covered in 1 minute will be recorded. Both assessments will be performed without orthoses, but a key-walker is allowed for the 1-minute walk test for children classified as GMFCS-level III.

6. Statistics

Descriptive statistics for all groups will be summarized using appropriate summary indices. The comparison between TD children and children with CP will be performed with a Student's *t*-test (after confirming equality of variances) or the Mann-Whitney *U*-test. Associations between muscle morphology measures, muscle strength and participant characteristics will be evaluated with univariate linear regressions followed by a multivariate linear regression using a backward approach. The linear regressions in the TD cohort based on an anthropometric variable will be used to define the deficits in muscle strength and muscle morphology in CP children.

To define the effects of the PRT intervention linear mixed models will be applied to evaluate the difference in evolution over time between the control and intervention group (time*group interaction effect) and between PRE and POST within each group (time effect). The random effects in these models can correct for the correlation between repeated observations within the same subject. Moreover, in the case of missing values that are completely at random, i.e. not related to any observed or unobserved outcomes, or at random, i.e. related to observed outcomes, linear mixed models provide valid inferences for missing observations. A covariance structure for repeated measurements to model longitudinal dependencies within the participant will be applied with a random intercept for participant (legs are nested within participants). The models will be adjusted for age and GMFCS level as covariates as these were used to allocate the children to the control or intervention group. Age was entered as a categorical variable (<8 years and >8 years). A full-factorial time*group mean model adjusted for age and GMFCS level, with a compound symmetry covariance matrix, unless an unstructured covariance matrix results in a better fit (Akaike information criterion decrease of >2). Adjustment for age (categorical variable: <8 years and >8 years) and GMFCS level will be included as these were used to allocate the children to the control or intervention group.

The α -level will be adjusted to $p \leq 0.01$ since multiple parameters are evaluated for most research questions, with a maximum of 5 parameters (functional strength). All analyses will be performed with SPSS (Version 28, SPSS Inc., Chicago, Illinois).

Finally, the data of the total intervention group (intervention + waitlist control group with delayed intervention) will be used to define the association between baseline properties and the changes in the outcome parameters after PRT with uni- or multivariate regression (mixed) models.

References

<https://doi.org/10.1016/j.jclinepi.2003.12.013>

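### Children are allocated before the PRE assessment and tested by assessors who know the group, so any allocation-driven difference specific to PRE would enter the time-by-group effect in full

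*Combined protocol and SAP*

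**What the plan says.** The Study design section fixes the order: "After enrollment and prior to the first assessment, participants will be assigned to the intervention or the control group through randomization by minimization". On awareness it says "Blinding is not completely possible since participants and trainers are aware of group allocation", and then "Assessors are also aware of group allocation during assessments". Neither statement is limited to POST. The section does not say when families learn the group. The nearest time marker is "Participants in the intervention group start training within 2 weeks after the baseline assessment".

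The same section gives three mitigations: data are anonymized before processing and analysis, a child has the same assessors at PRE and POST, and one processor handles all of a child's data. The isometric strength section adds a fixed dynamometer and standardized encouragement.

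On allocation, "MinimPy will be used to randomize the participants based on age" and GMFCS level; no PRE measurement is used. The Statistics section estimates the effect as the time-by-group interaction in a full-factorial mixed model adjusted for age category and GMFCS level.

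**The concern.** PRE is the one visit that could be measured before anyone knows the group, and the stated order gives that up. PRE is also half of the effect estimate. If a child tries less hard or harder at PRE because the group is known, or an assessor conducts or scores the test differently, the difference counts as change over time between the groups.

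Exposure is greatest where the result depends on effort or on how the test is run: maximal isometric contractions, the 30-second repetition tests, standing long jump, gross motor function and the 1-minute walk. The fixed dynamometer and standardized encouragement limit an assessor's influence on isometric strength, but they do not conceal the group. Muscle morphology does not depend on effort and is anonymized before processing, so it is exposed only while images are acquired.

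A PRE-specific shift could raise the false-positive rate or, if it runs against training, reduce power.

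**Working it through.** **Inputs from the documents.** Sample size section: d = 0.8, alpha 0.01, power 80%, 39 independent observations per group, design effect 1.1, "resulting in 43 clustered legs, or 22 bilaterally affected participants per group". Statistics section: interaction in a full-factorial model.

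**Inputs assumed.** The size and timing of any shift (in SDs of the outcome), the PRE-POST correlation r, equal SDs at both visits, and complete data. None of these is in the documents.

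**Step 1: reproduce the plan's figures.** A two-sided two-sample t-test (noncentral t) with d = 0.8 and alpha 0.01 has power 0.810 at 39 per group and 0.798 at 38, so 39 reproduces. The plan does not state sidedness; two-sided matches. Design effect: 1 + 0.1 × (2 − 1) = 1.1. Then 39 × 1.1 = 42.9, rounded to 43 legs, and 42.9 / 2 = 21.45, rounded to 22 children.

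**Step 2: how a PRE shift enters.** With complete data,

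interaction = (POST_I − PRE_I) − (POST_C − PRE_C).

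A between-group shift b present only at PRE contributes −b. A shift of equal size at both visits contributes zero. In general the net bias is the POST shift minus the PRE shift.

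A simulation of the planned model (39 per group, no true effect, PRE lowered by 0.30 SD in the intervention group, 150 runs per setting) gave a mean interaction of 0.30 at r = 0.5 and 0.31 at r = 0.8. Adjustment for age and GMFCS level did not remove it.

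**Step 3: size on the plan's scale.** Change has SD √(2(1 − r)) in units of the outcome SD, so the bias in d is (POST shift − PRE shift) / √(2(1 − r)). For 0.1 SD and r = 0.8: 0.1 / √0.4 = 0.158. Two-sided rejection rates with no true effect, alpha 0.01 (df 76 and 42), for PRE-only shifts:

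| PRE-only shift | r | bias in d (absolute) | 39 per group | 22 per group |
|---|---|---|---|---|
| 0.05 SD | 0.5 | 0.050 | 0.012 | 0.011 |
| 0.05 SD | 0.9 | 0.112 | 0.019 | 0.015 |
| 0.1 SD | 0.5 | 0.100 | 0.017 | 0.014 |
| 0.1 SD | 0.8 | 0.158 | 0.030 | 0.020 |
| 0.1 SD | 0.9 | 0.224 | 0.054 | 0.032 |

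The 22-per-group column applies to outcomes with one value per child (gross motor function, 1-minute walk, long jump, sit-to-stand, bilateral heel raise) if every child is bilaterally affected. If a 0.1 SD shift at r = 0.8 runs against training, power at 39 per group falls from 0.81 to 0.58, because the expected d becomes 0.8 − 0.158 = 0.642.

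**Step 4: present order versus allocation after PRE.** Type I error at r = 0.8, assuming that the later allocation removes the PRE shift and leaves the POST shift as it was:

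| PRE shift / POST shift (SD) | 39 per group: now → after | 22 per group: now → after |
|---|---|---|
| 0.1 / 0 | 0.030 → 0.010 | 0.020 → 0.010 |
| −0.1 / 0.1 | 0.113 → 0.030 | 0.059 → 0.020 |
| 0.2 / 0.1 | 0.030 → 0.030 | 0.020 → 0.020 |
| 0.1 / 0.1 | 0.010 → 0.030 | 0.010 → 0.020 |

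The later allocation increases bias when both shifts run in the same direction and the PRE shift is less than twice the POST shift. It reduces bias when the shift is PRE-only, when the shifts are opposite, or when the PRE shift is more than twice the POST shift.

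**The case against.** The strongest objection is that the benefit of re-ordering is not shown. The same assessors test a child twice, so a similar shift at both visits is plausible. That shift cancels now and would not cancel afterwards. The documents do not say which pattern applies. This stands as a real trade-off. It is still a weak reason to keep an unblinded baseline, because it relies on bias at one visit offsetting bias at another 12 weeks later, and nothing in the plan secures that.

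Second, every influential magnitude is assumed, and at 0.05 SD the type I error is only 0.011-0.019. This stands: the figures are illustrations.

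Third, the plan openly discloses that participants, trainers and assessors are aware of the group. This also stands, but disclosure and later anonymization do not undo what happened during a test.

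Fourth, few children may remain to benefit. The trial was designed in 2018, the document is dated 1 November 2021, and parts of it are in the past tense. The documents do not give recruitment status, so this limits the remedy to an unknown degree.

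A reader might infer that families certainly knew the group at PRE. That is likely but not stated. A reader might also infer that the result is biased in favour of training. The documents give no direction, and a shift could equally work against it.

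**Conclusion.** The point holds as avoidable exposure to bias. Two facts are stated: allocation precedes PRE, and assessors know the group during assessments with PRE not excepted. One consequence follows from the model: a PRE-specific shift passes into the effect undiminished. Whether such a shift exists, how large it is and which way it runs cannot be learned from the documents.

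Under an assumed PRE-only shift of 0.05 to 0.1 SD and r of 0.5 to 0.9, the type I error at nominal 0.01 is about 0.012-0.054 at 39 per group and 0.011-0.032 at 22 per group. The plan's sample size figures are unaffected. This is a cheap improvement to the design, not a demonstrated error in the result, and confidence is medium.

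**What to change.** For children not yet assessed, amend the Study design section so that MinimPy is run, and its result disclosed to families and assessors, only once PRE is complete. The minimization factors are age and GMFCS level, so nothing else in the allocation changes. For children already assessed, record that allocation preceded PRE and state this as a limitation. Keep stating that POST is unblinded.

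Costs and downsides:

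- The explanatory visit, consultation with the child's physiotherapist and programme set-up must fit the existing 2-week window between PRE and the start of training. The up to 3 familiarization sessions must fit too, if they count inside it, which the plan does not state.
- The amendment may have to go to both ethics committees (Leuven and Ghent).
- If recruitment is under way, two assessment orders are mixed in one small trial, so the order should be recorded for each child.
- POST stays unblinded, so a shift equal at both visits, which now cancels, would remain as a POST-only bias.

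### Does an 80% power figure counted in legs mislead for outcomes measured once per child?

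*Combined protocol and SAP*

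**What the plan says.** The Sample size section explains that no randomised trial of muscle-size change after this training was available for these children when the trial was designed. Effect sizes were therefore taken from reviews "reporting muscle strength outcomes after PRT were used", with values of 0.53, 1.050 and 1.105. The team chose d = 0.8, a type I error of 1% and 80% power for a t-test on change between arms, which gave 39 per group.

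A design effect for two legs in one child follows, with a correlation of 0.1: "the estimated design effect was 1.1, resulting in 43 clustered legs, or 22 bilaterally affected participants per group". The correlation is "based on literature of general health parameters", and the cited paper is titled "Patterns of intra-cluster correlation from primary care research to inform study design and analysis". The section closes with "A group including both uni- and bilaterally affected children would require a sample size between 39 and 43", and gives no unit for the two numbers.

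The outcome list is wider than leg measurements. Functional strength assessments has "repetition maximum tests including bi- and unilateral heel raise, sit-to-stand, and lateral step-up", and adds: "Explosive strength will be evaluated with a standing long jump, with both feet together". Gross motor function and walking capacity has a motor score and a walk test for which "the distance covered in 1 minute will be recorded".

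The Statistics section tests the time-by-group interaction in mixed models, with legs nested in participants. It sets the threshold at 0.01 because up to five parameters (functional strength) are tested together. No outcome is named as primary, and no share of bilaterally affected children is given.

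**The concern.** The step from 39 to 22 children works only if a bilaterally affected child supplies two partly independent values. Gross motor function, the 1-minute walk and the standing long jump supply one. On a natural reading so do the bilateral heel raise and sit-to-stand. For these a second leg adds nothing, and the sample is simply the number of children.

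The Sample size section never says that its 80% excludes such outcomes. The Statistics section applies the same 0.01 threshold without separating them, and the family that sets the threshold contains three of them. A reader could credit the trial with 80% power throughout and take a non-significant walking or jumping result as evidence of no effect.

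The second worry is the correlation. A value from primary care research is applied to two legs of one child, with no sensitivity range. If changes in the two legs move together more closely than 0.1 implies, even the leg-level 80% would be optimistic.

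**Working it through.** **Inputs from the Sample size section:** d = 0.8, type I error 0.01, power 80%, m = 2, correlation 0.1. The section does not state sidedness. A two-sided test reproduces its 39, whereas a one-sided test would need 33.

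**Reproducing the plan.** Power comes from the noncentral t with 2n − 2 degrees of freedom and noncentrality d × √(n/2).

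- n = 38 per group: 79.8%. n = 39: noncentrality 0.8 × √19.5 = 3.53, power 81.0%. So 39 is the smallest sufficient number.
- Design effect: 1 + 0.1 × (2 − 1) = 1.1.
- Legs: 39 × 1.1 = 42.9, rounded up to 43.
- Children, if all are bilateral: 42.9 / 2 = 21.45, rounded up to 22.

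All three printed figures hold.

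**Unit of the closing range.** If an all-unilateral group needs 39 children and an all-bilateral group needs 22, a mixed group needs between 22 and 39 children. A range of 39 to 43 is therefore coherent only as legs.

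**One-value-per-child outcomes.** Here n is the number of children. Two assumptions go beyond the document: d = 0.8 carried over to these outcomes, and, for the middle row, half the children bilateral. That row's count is 39 / (0.5 × 2/1.1 + 0.5) = 27.7, rounded up to 28.

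| Children per group | Power at d = 0.8 | d detectable with 80% power |
|---|---|---|
| 39 (all unilateral) | 81% | 0.79 |
| 28 (half bilateral, illustrative) | 63% | 0.94 |
| 22 (all bilateral) | 49% | 1.07 |

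If the closing range meant children after all, 39 to 43 per group would give 81% to 86% and the difficulty would vanish.

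**Two-leg outcomes under other correlations.** With 22 bilateral children, the effective n is 44 / (1 + ρ), tested on 42 degrees of freedom. With 28 children, half bilateral, it is 28 / (1 + ρ) + 14, on 54 degrees of freedom. Every ρ above 0.1 is an assumption.

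| ρ | 22 bilateral children | 28 children, half bilateral |
|---|---|---|
| 0.1 | 80.5% | 81% |
| 0.3 | 72% | 76% |
| 0.5 | 64% | 71% |
| 0.8 | 54% | 66% |

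The loss becomes material from about 0.3. The document offers no estimate of the between-leg correlation of change that would place the truth there.

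**What the 80% is attached to.** The reason for the calculation is muscle size, the effect sizes are for muscle strength, and the counting unit is the leg. None of these describes a walk distance, a motor score or a two-footed jump, and the plan states no power or effect size for those.

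**The case for a change.** The best case for a change is that the scope is implied and never written. The plan ranks no outcomes and uses one threshold for all of them. The 49% needs no assumed mix, because 22 children is the plan's own printed case. A sentence on scope, a detectable effect for per-child outcomes, a range of correlations and a unit for the closing range would cost no enrolment and leave the model untouched.

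Some of this stands. The scope and the unit could have been written out, and a low-powered null result should not be read as absence of effect. But the additions would correct no figure and alter no analysis. Power for per-child outcomes also cannot be pinned down from the document: it depends on an unstated bilateral share and on an effect size borrowed from strength reviews. The correlation range is a sensitivity request about an input not shown to be wrong.

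A scope sentence could even introduce an error. Participant characteristics defines a most affected leg for bilaterally affected children, while Statistics nests legs within participants. Writing that both legs are analysed would settle that question without support. If only one leg were analysed, the per-child figures would apply to strength and morphology as well. That is a separate question about the unit of analysis, and wording about power does not resolve it.

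**Conclusion.** No change follows. The sample size arithmetic is correct, and its context places the 80% on leg-level strength and muscle size, so the plan makes no power claim for walking, gross motor function or the long jump that the design then fails to meet.

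For one-value-per-child outcomes, power would lie between 81% (39 children per group) and 49% (22), with a detectable d between 0.79 and 1.07. This rests on reading the closing range as legs, on a two-sided t-test at 0.01 and, for the power figures, on an assumed d = 0.8. The 63% at 28 children is an illustration. The planned mixed model, adjusted for age and GMFCS level, may differ somewhat from the t-test.

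An analyst can fill the gap sensibly: read the 80% as a leg-level figure, and judge per-child results by their estimates and precision rather than by the design power. The correlation of 0.1 remains an untested planning input, with no demonstrated error.
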